5.0 Procedures Involved

5.1 Study Design:

Mixed methods is generally defined as the collection and analysis of both quantitative and qualitative data that links these two forms of data concurrently, sequentially, or embedded one into another.^{57,58} Among the various rationales for conducting mixed methods research are: a) to better understand a research problem by converging numeric trends from quantitative data and specific details from qualitative data; and b) to obtain statistical, quantitative data from a sample of a population and use them to identify individuals who may expand on the empirical results through qualitative findings.⁵⁹ Few evaluations of ADRD caregiver interventions have combined qualitative and quantitative data to obtain a greater understanding of why certain protocols are beneficial or not. For these reasons, an embedded experimental mixed methods design will be utilized for the proposed demonstration. An embedded experimental mixed methods design combines the collection and analysis of qualitative data within a traditional randomized controlled trial (RCT) design; the collection of the embedded qualitative data may occur prior to, during, or after the

RCT.^{57, p. 90} The embedded experimental design will assist the research team examine the process of eNeighbor's implementation during the conduct of the RCT and determine why and how the eNeighbor worked or did not for ADRD caregivers following the completion of the RCT (see Figure 1).^{57,60-63}

5.2 Study Procedures:

Recruitment. The Principal Investigator (PI) or research coordinators (RCs) will initiate email, telephone, or mail contact with ADRD caregivers on the University of Minnesota Caregiver Registry (IRB# 1007S85812) or others recruited by the PI (see above) who potentially meet the project inclusion criteria. In addition, the PI or RCs will ask professional caregivers on the Registry to identify potential ADRD caregivers for recruitment purposes (this will also occur via the various other recruitment and outreach activities noted above). During initial enrollment contacts, the PI or RCs will describe the eNeighbor monitoring system, explain study procedures, and invite potential ADRD caregivers to participate. Caregivers will be offered the opportunity to ask any questions about the study procedures. The Telephone and Email script will be utilized. =

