These recruitment efforts will be facilitated by the Minnesota Board on Aging (MBA), the Minnesota-North Dakota Alzheimer's Association regional office, and other organizations. The MBA will help us promote this study through Area Agencies on Aging, many of which serve ethnic and racially diverse older adults as well rural ADRD caregivers. Specifically, the Information Sheet will be distributed to the MBA and associated Area Agencies on Aging in Minnesota, the Minnesota-North Dakota Alzheimer's Association, or other organizations to distribute to family members or family members of clients that these organizations serve. The Information Sheet is also used as the basis for any other advertising efforts or by other organizations who wish to reach out to their clients and families regarding this opportunity. Finally, a Letter to Families can be sent to organizations if they wish to distribute to their clients or family members of clients.

Additional recruitment efforts may occur, on an as-needed basis, via the PI's or RC's community outreach efforts. The PI, via the annual Caring for a Person with Memory Loss conference (see <https://www.sph.umn.edu/events-calendar/caring-for-person-with-memory-loss-conference/>) and a number of other community presentations, will have the opportunity to recruit potential participants. Following an overview of the study procedures, the PI or RC will provide interested participants with a Documentation of Permission form to complete, which will provide the PI and research team members to contact the potential participant to determine eligibility and proceed with enrollment. If independent living settings or similar residential providers are willing to collaborate with the research team to identify potential participants, we ask them to: a) distribute via email or print the study flyer, information sheet, letter to families, and/or other recruitment information to announce the study and its availability; b) approach residents or family members to discuss the study, and if there is interest, obtain permission for [name] or his team to follow-up and contact them to initiate the recruitment and enrollment procedure; and c) setting liaisons will simply forward potentially interested family members' contact information to [name] to do so.

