Eligibility screening. If caregivers agree to participate, the PI or RC will initiate a brief screening procedure. The following inclusion criteria will be applied for persons with ADRD: 1) English speaking; 2) physician diagnosis or recognition of ADRD (e.g., Alzheimer's disease, Lewy Body disease, fronto-temporal dementia, or stroke/vascular dementia; mild cognitive impairment); 3) not currently receiving care or case management services; and 4) 55 years of age and over.

PROTOCOL TITLE: A Proactive Health Monitoring Intervention for Dementia Caregivers: The eNeighbor

Caregivers of persons with ADRD must: 1) speak English; 2) be 21 years of age and over; 3) self-identify as someone who provides help to the person with ADRD because of their cognitive impairments; 4) self-identify as the person most responsible for providing hands-on care to the person with ADRD or sharing that role with someone else (i.e., the “primary” family caregiver, which can include highly involved kin or non-kin of persons with ADRD; those who share care responsibilities are also eligible); 5) plan to, or ideally wish to, remain in the area for at least 18 months in order to reduce possible loss to follow-up; and 6) indicate a willingness and need to use eNeighbor. To determine eligibility, the E-Neighbor Screening Form will be administered either in-person over the telephone by the PI or RC to determine and identify eligible persons with ADRD and their family caregivers.

Enrollment/Consent and Assent

Within two weeks following the completion of eligibility screening, consent/assent procedures and baseline interviews will be scheduled within 2 weeks for eligible caregivers. Signed informed consent from the eligible family caregiver will take place. Signed informed consent will be offered in-person, via mail, or if deemed most convenient to the family caregiver, via an online consent form.

If a legally authorized representative (LAR) for the person with ADRD is identified other than the family caregiver, we will also obtain signed consent from this individual. For the purposes of efficiency, we will offer an online consent form to review and approve. All online consent and HIPAA forms will be administered via the secure University of Minnesota Google Docs application.

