In addition to administering informed consent forms to family caregivers and LARs, we will additionally provide HIPAA forms (either in-person or via mail and online formats) for the family caregiver and LAR to review and sign. To complete this procedure, the Family Caregiver Consent Form, the LAR Consent Form, and the HIPAA form will be utilized.

Following the securing of consent of primary caregivers and LARs, Verbal Assent of persons with ADRD will take place (see supplemental documents uploaded to IRB). While ideally this may take place simultaneously with the consent procedures above, there may be a delay in time (hopefully no more than several days) between when consent is secured from family caregivers and LARs and assent of the person with ADRD.

Baseline

As soon as possible following the completion of consent, HIPAA, and verbal assent, the baseline survey/interview will take place. The survey/interview will ask the family caregiver to complete a survey that will ask questions about the family caregiver, the person with ADRD, and the person with ADRD’s and family caregiver’s memory loss’ emotional, psychological, physical health, the caregiver’s confidence about their care situation. The survey/interview we will also ask the family caregiver about various health events that the person with ADRD may have experienced. The baseline survey can occur in-person, in the family caregiver’s home, Mayo Building at the

PROTOCOL TITLE: A Proactive Health Monitoring Intervention for Dementia Caregivers: The eNeighbor

University of Minnesota, or another location of the family caregiver's choosing. A mail survey, telephone interview, or online survey will also be arranged if that is easier for the family caregiver. If the caregiver elects to complete the online version of the survey, the survey link will be emailed to the caregiver. To complete this procedure, the Baseline eNeighbor Survey will be utilized.

Treatment/Intervention Period

Following the completion of baseline interviews, ADRD caregivers will be randomly assigned to an eNeighbor treatment condition that receives the multi-sensor, remote monitoring system or an attention control group. Randomization (participant is assigned to either the treatment or control condition) will be completed via an a priori list generated from <http://randomizer.org> by the PI. The PI will inform the ADRD caregiver of their randomization status within 2-3 days following completion of the baseline interviews.

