The PI or research coordinators will call caregivers in the control group 48 hours following assignment to the usual care control group to address any questions they may have and to thank them for being part of the study and volunteering their time if no response from the participant in the usual care group is received following randomization). Group allocation (either attention control or treatment condition) will be based solely on their a priori randomization assignment number. The PI or research coordinators will then inform the ADRD caregiver of her/his group assignment within 2 days of baseline survey completion.

Following ADRD caregivers' enrollment into the proposed project and within 2 weeks of randomization to the eNeighbor treatment condition, the Director of Nursing and Technology (DNT) will schedule a visit at the home of the person with ADRD and the enrolled family caregiver. The DNT will oversee all system maintenance (battery changes, troubleshoot in instances where there is a loss of system contact), establish arrangements for other care services that are needed for the person with ADRD in instances of eNeighbor alerts or other health-related transitions, and develop and monitor a care plan with the family caregiver to ensure that it is effectively followed.

An initial Needs Assessment takes place to determine the best use and deployment of the eNeighbor remote sensor technology in the person with ADRD's home. The assessment begins with an identification of risk factors that suggest the need for remote health monitoring (e.g., the person with ADRD lives alone and has little supervision; the caregiver needs support; the person with ADRD has a history of falls or the caregiver has concerns with falls) as well as the use of other monitoring systems such as Safe Return™ or a similar device. The DNT will then discuss the results of the needs assessment with the ADRD caregiver and review how the remote monitoring system works, that the eNeighbor does not include cameras or microphones, is secure, and is private, and that the system learns the normal activities of the person with ADRD and alerts both the family caregiver and the DNT if something appears unusual (e.g., absence of expected ADL behaviors). Following this operational overview, the DNT will summarize the secure and password-protected MyHealthsense website, which is used by the family caregiver or other

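### The PI makes the whole randomization list in advance and also recruits and may screen families, and no concealment step is described

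*Combined protocol and SAP*

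**What the plan says.** Section 5.2 (Treatment/Intervention Period) states that randomization "will be completed via an a priori list generated from" a public web randomizer, and names the PI as the one who generates it. The next paragraph adds: "Group allocation (either attention control or treatment condition) will be based solely on their a priori randomization assignment number". Assignment follows consent and the baseline interview.

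The PI is also active at the front of the pathway:

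- **Contact.** Section 12.1 has the PI initiating contact with caregivers on the University registry. Section 5.2 (Recruitment) says: "During initial enrollment contacts, the PI or RCs will describe the eNeighbor monitoring system, explain study procedures, and invite potential ADRD caregivers to participate".
- **Outreach.** The PI, through an annual conference "and a number of other community presentations, will have the opportunity to recruit potential participants".
- **Screening.** The screening form is "administered either in-person over the telephone by the PI or RC to determine and identify eligible persons with ADRD" and their caregivers. One caregiver criterion in section 5.2 asks for a stated need for the system as well as a wish to use it.

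Other passages narrow the PI's control. Section 12.3 says participants identify themselves and that, outside the registry, enrolment relies on them to make contact. In residential settings, "setting liaisons will simply forward potentially interested family" members' contact details to the study team. On timing: "Within two weeks following the completion of eligibility screening, consent/assent procedures and baseline interviews will be scheduled within 2 weeks for eligible caregivers". On the mode of the baseline survey: "A mail survey, telephone interview, or online survey will also be arranged if that is easier for the family caregiver".

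**The concern.** Randomization protects a comparison only if those who bring participants in cannot tell which arm comes next. A sequence written in advance by a recruiter is known to that recruiter unless something prevents it. With that knowledge, a family thought likely to do well, or in greater need, can be approached sooner, judged eligible more readily, encouraged more warmly, or scheduled so as to fall on one arm. None of this need be deliberate.

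The arms could then differ in need or motivation before treatment starts. The primary outcome is caregiver self-efficacy and competence (section 3.1), reported by caregivers in surveys, and motivation could plausibly affect it. The cost comparison in section 17.3 (Hypothesis 4) argues explicitly from the randomized design when it tests the difference in mean costs, so it depends on the same protection.

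**Working it through.** No figure in the plan is in dispute, so the check sets the steps of the pathway side by side.

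| Step | Who acts | What could vary with a known assignment | What limits it |
|---|---|---|---|
| List made | PI alone (5.2) | – | No transfer of custody or viewing restriction described |
| Approach | PI or coordinators (5.2, 12.1, 12.3) | Who is contacted, and when | Self-identification; outside organisations; setting liaisons |
| Screening | PI or a coordinator (5.2) | Judgement of need for the system | The other criteria are more factual |
| Consent and baseline | Arranged by the team (5.2) | Encouragement; order of scheduling | Two-week scheduling limit; caregivers partly control when a mail or online baseline is finished |
| Assignment | List number only (5.2) | Little, once the number is attached | Allocation rests solely on the number |
| Disclosure | PI in one paragraph, PI or coordinators in the next (5.2) | Too late to affect entry | 2-3 days after baseline in one paragraph, 2 days in the next |

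1. **Can the PI know the sequence?** Yes, on the text as written. The PI makes the list, and no envelope, central service, separate holder or access limit is described. The coordinators' access is not stated either way.

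2. **Can the PI link a position to a family?** This depends on when the number is attached, which is not stated. If it is attached at screening or consent, the link is direct. If it is attached only when the baseline is completed, the PI must anticipate the order of completion, so the foresight is less exact. Neither case excludes it.

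3. **Does assignment after baseline close the route?** It limits altering an assignment once made. Approach, eligibility judgement, encouragement and scheduling all come earlier, so they remain open.

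4. **Is exposure confined to enrolled families whom the PI handles?** No. Selection also works through families who are not approached, not encouraged or not judged eligible, and they are not among the 200. If the coordinators see the list, their contacts count too.

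5. **Does the analysis repair it?** In part. Section 17.3 includes the baseline value as a covariate in one set of evaluations. It also tests context-of-care, primary-stressor and resource covariates for group differences and carries significant ones into all tests. The Cox models add stress-process covariates. Some need is therefore measured, since the primary stressors index dementia severity (section 2.3). Need and motivation that are not measured stay outside every one of these adjustments.

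6. **Can a size be given?** No. It would require knowing who could see the list, when numbers were attached, how many approaches and eligibility decisions were made with that knowledge, and how far they shifted prognosis. The documents give none of these. The planned 100 + 100 = 200 does not help, because selection bias does not shrink as the sample grows.

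**The case against.** The best reply is that the route is narrow. Coordinators share the work, many families come forward themselves or through outside bodies, scheduling has a two-week limit, caregivers partly set their own baseline date, and matching a family to a list position is uncertain. All of this stands. It makes exploiting the list harder, but it does not hide the list.

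A second reply is that silence is not absence. Some pages were not in the text supplied for review, and a custody arrangement might be described there. The point is therefore limited to the supplied text. That text does include the part of section 5.2 that sets out randomization, where such a step would be expected, and it contains none.

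A third reply is that the trial may be over. Section 8.1 ends the project on 3/30/2019, and section 6.1 reads as a late version. That changes the remedy from redesign to reporting.

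Three stronger readings are tempting, and the documents do not support them:

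- A reader might infer that the PI did look ahead, or that the results are biased. Nothing in the documents says so; they show an opportunity only.
- A reader might infer that the coordinators also know the sequence. Their access is simply not stated.
- A reader might infer that assignments could be switched afterwards. Allocation by number alone, after baseline, points the other way.

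**Conclusion.** The point holds as a gap in the protection of the between-arm comparisons. The plan gives list generation to a person who also recruits and may screen, and the supplied text describes nothing that conceals the sequence from that person. A route to selection bias is open at approach, eligibility judgement, encouragement and scheduling. Its size cannot be estimated, and no claim is made that bias occurred or that the trial is invalid.

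The conclusion rests on two assumptions: that pages not supplied contain no concealment procedure, and that the PI retains the list after making it. If either is wrong, the remaining task is to say so in section 5.2. The matter should be fixed because it bears on every randomized comparison and is cheap to repair.

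**What to change.** **If enrolment is open**

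- Have someone with no part in recruitment, screening or outcome collection generate and hold a fresh list for the remaining assignments. A locked randomization module in a system the university already provides would also serve, if one is available. Handing over the existing list is not enough, because the PI has already had it.
- Release each assignment singly, only after eligibility, consent and baseline are logged as complete. The PI and coordinators should see released assignments only.
- Keep release within the protocol's disclosure window, and reconcile the two versions of that window in section 5.2 (2-3 days and 2 days after baseline).
- State in section 5.2 who holds the list and when a number is attached to a family.

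The cost is a protocol wording change, a small administrative task for a holder who must be found and agree, and a short wait per assignment. No extra participants or visits are needed.

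**If enrolment is complete**

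- Report who generated the list, who could see it, and when numbers were attached.
- State the lack of described concealment as a limitation on the between-arm comparisons, including the cost comparison.

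The cost is a few sentences.

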6.0 Data Banking

6.1 Storage and Access: The original intention was to make the datasets generated and/or analyzed publically available upon completion of primary or secondary outcome analyses. However, in consultation with the Institute for Social Research at the University of Michigan, which houses the National Archive of Computerized Data on Aging (NACDA), it was determined that the language in the consent forms (which were originally developed at the outset of the project in 2014) did not support data

sharing of any sort. The datasets generated and analyzed during the current study are not, and will not be, publicly available as originally planned. According to the study's consent forms, data can only be viewed and analyzed by the principal investigator's research team.

6.2 Data: Only de-identified data will be stored, but not publically shared [see section 6.1].

7.0 Sharing of Results with Participants

7.1 Sharing of Results with Participants: We will create a summary page and brief videos highlighting study results/findings for participants.

8.0 Study Duration

8.1 ADRD caregivers will participate in the study for 18-months; the total project duration is 5 years (3/31/2014-3/30/2019). A project timeline is below:

	Months 1-3	Months 4-12	Months 13-55	Months 55-60
Data management processes, team training	●	○	○	○
Project and Community Advisory Board meetings	●	●	●	●
Recruitment of ADRD caregivers (n = 200)	○	●	●	○
Home installation and training of e-Neighbor		●	●	○
Baseline, 6-, 12-, and 18-month data collection		●	●	●
Embedded treatment fidelity/process evaluation		●	●	●
Embedded post-RCT semi-structured interviews			●	●
Quantitative, qualitative, and mixed analysis			●	●
Dissemination				●

NOTE: ADRD = Alzheimer's disease or a related dementia; RCT = randomized controlled trial;

● = primary focus; ○ = ongoing but less intensive

9.0 Study Population

9.1 Inclusion Criteria:

The following inclusion criteria will be applied for 200 persons with ADRD: 1) English speaking; 2) physician diagnosis of ADRD (Alzheimer's disease, Lewy Body disease, fronto-temporal dementia, or stroke/vascular dementia; mild cognitive impairment only); 3) not currently receiving care or case management services; and 4) 55 years of age and over. Caregivers of persons with ADRD must: 1) speak English; 2) be 21 years of age and over; 3) self-identify as someone who provides help to the person with ADRD because of their cognitive impairments; 4) self-identify as the person most responsible for providing hands-on care to the person with ADRD; 5) plan to remain in the area for at least 18 months in order to reduce possible loss to follow-up; and 6) indicate a willingness to use eNeighbor.

9.2 Exclusion Criteria: Anyone who does not fit the inclusion criteria will be excluded.

9.3 Screening: If caregivers agree to participate, the PI or research coordinators will initiate a brief screening procedure applying the inclusion criteria above.

